1 STUDY SYNOPSIS

Study title

Effects of single doses of tobacco-based snus and 3 mg nicotine pouches on plasma nicotine, pharmacokinetics, and pharmacodynamics.

Study code	Planned study period
SM24-03	Q1 2025 to Q3 2025

Coordinating/Principal Investigator

[name] CTC Clinical Trial Consultants AB [name], Sweden

Study design

This is a multi-center, open-label, randomized, 5-way cross-over, single-dose administration study designed to assess nicotine exposure from three nicotine pouch (NP) products compared to two tobacco-based products. The investigational products (IPs) include two flavored NP products (both 3 mg), one unflavored NP product (3 mg), and two tobacco-based snus products (4 mg and 8 mg).

Objectives and endpoints

Primary objective	Endpoint
To demonstrate the similarity in C_{max} between each of the three NP products and at least one of the two tobacco-based products.	Similarity in baseline-adjusted C_{max} based on nicotine plasma concentrations after administering single doses of the three NP products and the two tobacco-based products.

No.	Secondary objectives	No.	Endpoints
1.	To demonstrate equivalence in C_{max} and AUC _{0-inf} between each of the three NP products and at least one of the two tobacco-based products.	1.	Equivalence (90% CI for the ratio between 0.8 and 1.25) in baseline-adjusted C_{max} and AUC_{0-inf} based on nicotine plasma concentrations after administering single doses of the three NP products and the two tobacco-based products.
2.	To compare the in vivo extracted amount (mg/unit) and extracted fraction (%) of nicotine from the three NP products with those from the two tobacco-based products	bunt (mg/unit) and extracted extracted fraction (%) of nicotine between the three products with those from extracted fraction (%) of nicotine between the three products and the two tobacco-based products.	
3.	To compare the PK profile between the three NP products and the two tobacco-based products.	3.	The difference between the three NP products and the two tobacco-based products in the non-adjusted and baseline- adjusted PK parameters: AUC_{0-inf} , C_{max} , T_{max} , $AUC_{0-1.5h}$, AUC_{0-1ast} , and $T_{1/2}$.
4.	To assess the PD effects, measured as pulse rate and subjective outcome measures, of the three NP products and the two tobacco-based products.	4a.	PD (pulse rate): The difference between the three NP products and the two tobacco-based products for E_{imax} , T_{Eimax} , $E_{max0-60}$, and $T_{Emax0-60}$ in pulse rate, measured using a pulse oximeter after IP use.
		4b.	PD parameters: The difference between the three NP products and the two tobacco-based products for E_{dmax} and T_{Edmax} in the subjective parameter "craving" measured using a 100 mm VAS after IP use.

		4c.	PD parameters: The difference between the three NP products and the two tobacco-based products for E_{vmax} and T_{Evmax} in the subjective parameter "satisfaction", measured using a 100 mm VAS after IP use.
		4d.	PD (subjective outcome parameters): The difference between the three NP products and the two tobacco-based products for the subjective parameters "product-liking" and "intent to use again", measured using a 100 mm VAS 30 min after IP use.
5.	To evaluate the safety and tolerability of the three NP products and the two tobacco-based products by administering single doses in current, daily oral tobacco/NP users.	5.	Frequency, intensity, and seriousness of AEs.
No.	Exploratory objectives	No.	Endpoints
1.	To evaluate the impact on "product-liking" vs. the subjects' usual oral tobacco/nicotine product of choice by administering single doses of the three NP products and the two tobacco-based products.	1.	The difference in "product-liking" vs. the subjects' usual oral tobacco/nicotine product of choice between the three NP products and the two tobacco- based products measured on a 3-point scale using a MCQ 30 min after IP use.
			The difference in nicotine extraction normalized

AE=adverse event, AUC=area under the plasma concentration vs. time curve, AUC_{0-inf} AUC from 0 to infinity, AUC_{0-last} AUC from 0 to time of last measurable plasma concentration, AUC_{0-1.5} AUC from time 0 to time 1.5 hours, CI=confidence interval, C_{max} =maximum observed concentration, E_{dmax} =largest decrease from baseline, E_{imax} =highest increase from baseline, E_{max} -form time 0 to 60 min, E_{vmax} = largest value, IP=investigational product, MCQ=Multiple choice question, NP=nicotine pouch, PD=pharmacodynamic, PK=pharmacokinetic, T_{Edmax} =time to the first instance of E_{dmax} , T_{Eimax} = time to E_{imax} , $T_{Emax0-60}$ =time to $E_{max0-60}$, T_{max} =time of occurrence of C_{max} , T_{Evmax} = time to the first instance of E_{vmax} , VAS=visual analog scale.

Number of subjects planned

Approximately 76 subjects are planned to be screened to achieve 43 randomized subjects and at least 38 evaluable subjects, *i.e.*, subjects who have received all five IPs and have reliable C_{max} values for all IPs.

An effort will be made to ensure at least 17 of the randomized subjects (approximately 40%) are female. However, a minimum of 9 female subjects (approximately 20%) will be considered acceptable.

Diagnosis and main eligibility criteria

Healthy male or female subjects aged ≥ 21 to ≤ 60 years may be considered for participation in the study. These subjects should have used oral tobacco/NP products for ≥ 1 year and have a minimum daily consumption of five pouches. Furthermore, they should be willing and able to use both tobacco-based products and NPs. All subjects must be willing to comply with study procedures and provide written informed consent.

Subjects will be excluded from the study if they are pregnant, breastfeeding, or intend to become pregnant during the study. Subjects with a history or presence of diagnosed hypertension or cardiovascular disease will also be excluded. The same applies to subjects with any other medical condition that may interfere with the evaluation of the IPs or may put the subject at risk because of

participation in the study. Subjects intending to stop using nicotine-containing products will also be excluded from the study.

Methodology

Subjects will report to the clinic for a screening visit followed by five IP use visits (Visits 2-6) on separate days.

The screening visit (*Visit 1*) will take place within 4 weeks prior to the start of Visit 2 and will include an eligibility check, including evaluations of smoking and oral tobacco/nicotine use, collection of medical history, a brief physical examination, serology tests, electrocardiogram (ECG), vital signs (pulse rate and blood pressure), height, weight, and body mass index (BMI) assessments.

Prior to each IP use visit (Visit 2-6), subjects will abstain from tobacco/nicotine products as well as smoking (cigarettes or e-cigarettes) for >12 h. All treatment sessions will be performed during the morning hours (08:00 to 12:00) to facilitate abstinence.

At Visit 2 (Day 1), eligible subjects will return to the study site. The IPs will be administered as single pouches in a pre-determined randomized order. Subjects will keep the pouch still between the upper lip and gum for 30 min and will be instructed not to manipulate the pouch with the tongue or lips. They will also be instructed not to eat, drink, chew gum, or brush their teeth for 30 min before, during, and 30 min after IP use.

After 30 min, each used pouch will be collected and frozen (-20°C) pending analysis of residual nicotine content. Unused pouches from the same batch will serve as references and will be stored at - 20°C pending analyses.

Blood samples for the assessment of nicotine plasma levels and PK parameters will be collected at pre-defined time points from pre-use to 6 h after each IP use. The PD effects of the IPs will be determined using pulse rate measurements and subjective parameters (using VAS questions) at the same pre-defined time points as well as an MCQ 30 min after IP use.

AEs will be collected through subject interviews and will also include any AEs reported spontaneously by the subjects, starting from the initiation of IP use, and continuing until the last IP use visit (Visit 6).

Visits 3 to 6 will follow the same schedule as Visit 2. Each visit will be scheduled on separate days, preferably with at least 24 h between visits. However, it is acceptable to have visits on consecutive days, as long as all visits are not scheduled consecutively.

Investigational products and dosage

IPs	Nicotine content per pouch
NP 1 –Dry, flavor A	3 mg
NP 2 – Moist, flavor B	3 mg
NP 3 – Moist, unflavored	3 mg
T1 – Tobacco-based snus 1	4 mg
T2 – Tobacco-based snus 2	8 mg

Duration of investigational product use

The participating subjects will receive IPs on five occasions, in a cross-over fashion, with 30 min of IP use per occasion.

Duration of each subject's involvement in the study

Each subject will participate in the study for a period of approximately 3 weeks, not including the preceding 4-week screening period.

Pharmacokinetic assessments

Blood samples for analysis of PK parameters will be collected pre-use, and at 5 min, 10 min, 15 min, 20 min, 30 min, 40 min, 60 min, 1 h:30 min, 2 h, 4 h, and 6 h post-use. The PK parameters in the study will include AUC_{0-inf} , AUC_{0-last} , $AUC_{0-1.5h}$, C_{max} , T_{max} , and $T_{1/2}$.

Pharmacodynamic assessments

The PD effects will be assessed by measuring pulse rate and subjective parameters (using VAS) from pre-use (10 min prior to IP use) to 6 h post-use, at pre-defined time points. The subjective parameters that will be assessed are "craving", "satisfaction", "product-liking", and "intent to use again". In addition, "product-liking" vs. the subjects' usual oral tobacco/nicotine product of choice will be assessed using a 3-point scale questionnaire at 30 min post-use.

Nicotine extraction assessment

Used pouches will be collected after 30 min of use for the determination of residual nicotine in the IPs. The extracted amount (mg/unit) and extracted fraction (%) of nicotine will be assessed.

Safety assessments

AEs will be collected through subject interviews and will also include any AEs reported spontaneously by the subjects, starting from the initiation of IP use (Visit 2) and continuing until the last IP use visit (Visit 6).

Statistical methods

Using a coefficient of variation (CV) of 35%, based on previous studies, a power of 80%, a significance level of 10%, and lower and upper equivalence bounds of 0.8 and 1.25, with a null ratio of 1, 38 evaluable subjects will be needed. Assuming a dropout rate of 10%, a total of 43 subjects will be randomized.

Continuous data will be presented in terms of evaluable and missing observations, arithmetic mean, standard deviation (SD), median, minimum and maximum value, Q1-Q3 (interquartile range [IQR]). In addition, for the parameters AUC and C_{max} , the geometric mean and CV will be presented.

Categorical data will be presented as counts and percentages. When applicable, summary data will be presented by IP, and by assessment time. Individual subject data will be listed by subject number, IP, and, where applicable, by assessment time.

All descriptive summaries and statistical analyses will be performed using the statistical analysis software (SAS) Version 9.4 or later (SAS Institute, Inc., Cary, NC).

Baseline will be defined as the last non-missing data collection time point prior to each IP use.

Generally, no imputation of data will be performed. In case of missing start and stop times of AEs that cannot be investigated further, missing data will be imputed according to a worst-case scenario, *i.e.*, the start time will be imputed as the closest time point post intake of IP and end time as 23:59, resulting in the longest possible treatment-emergent duration of the AE.

No adjustment for multiple comparisons will be made. All formal comparisons will be made toward a designated reference product, and all significant findings will be reviewed for medical relevance. Spurious data will be evaluated continuously through data validation and, if connected to protocol deviations, evaluated case-by-case at the latest prior to the declaration of clean file and database lock.

Deviations from the original statistical analysis plan (SAP) will be described in the clinical study report (CSR).

Methods for handling missing, unused, and spurious data will be further specified in the SAP.

Study reporting

After completion of the study, an International Council for Harmonisation of Technical Requirements for Pharmaceuticals for Human Use (ICH) E3 guideline-compliant CSR will be prepared.

2 T	ABLE OF CONTENTS	
1	STUDY SYNOPSIS	2
2	TABLE OF CONTENTS	7
2.1	List of tables	11
2.2	List of figures	11
3	LIST OF ABBREVIATIONS AND DEFINITION OF TERMS	12
4	IMPORTANT MEDICAL PROCEDURES TO BE FOLLOWED BY THE INVESTIGATOR	15
4.1	Medical emergencies contact	15
5	INVESTIGATOR AND STUDY ADMINISTRATIVE STRUCTURE	16
6	INTRODUCTION	18
6.1	Background	18
6.2	Study rationale	18
6.3	Risk/benefit assessment	19
6.3.1	Risk assessment	19
6.3.2	Benefit assessment	19
6.3.3	Risk/benefit conclusion	20
7	STUDY OBJECTIVES AND ENDPOINTS	21
7.1	Primary objectives and endpoints	21
7.2	Secondary objective and endpoints	21
7.3	Exploratory study objectives and endpoints	23
8	STUDY DESIGN	24
8.1	Overall study design and schedule of events	24
8.2	Rationale for study design	28
9	STUDY POPULATION	29
9.1	Recruitment	29
9.2	Screening and enrollment log	29
9.3	Number of subjects	29
9.4	Inclusion criteria	29
9.5	Exclusion criteria	30
9.6	Restrictions during the study	31
9.6.1	General restrictions	31
9.6.2	Prior and concomitant therapy	31

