17.2 Determination of sample size

The sample size is calculated assuming a 2x2 crossover design analyzed on log scale, using the proposed analysis model outlined under Section 17.7.1. Specifically, the expected model estimates for the equivalence between NP 1 and at least one of the two tobacco-based products are used for the power calculation (Table 17.2-1).

Input	Value	Comment
Power	>80%	Refer to the reasoning presented below this table.
Alpha	10%	Nominally set. Inference is drawn based on a 90% CI.
Hypothesized true geometric least square means ratio	0.95	
Equivalence bounds for the geometric least square means ratio	0.8 to 1.25	
Coefficient of variation	0.35	As observed in previous studies.
Assumed drop-out rate	10%	
Total sample size	43	I.e. , 43 subjects to be randomized to achieve 38 evaluable subjects for the first secondary endpoint given the assumptions above.

Table 17.2-1 Power calculation

The calculation outlined in Table 17.2-1 above renders an 80% power for one comparison of NP 1 and one of the tobacco-based products. However, as defined in the first secondary objective/endpoint, two comparisons per NP product will be made (one to each of the tobacco-based products) with the understanding that the objective is fulfilled for a specific NP product if equivalence is demonstrated to one of the tobacco-based products.

Let T1 - T2 denote the event that equivalence is found between NP 1 and tobacco products 1 and 2. The probability of demonstrating equivalence between NP 1 and at least one of the tobacco-based products can then be written as:

$1 - P(\overline{T1}) * P(\overline{T2}|\overline{T1})$

As evident by this expression, the actual power in the study will be higher than 80%. However, the conditional probabilities of the complement of T2 is unknown, due to its correlation to the preceding comparison. Therefore, the exact power cannot be determined, with the extreme scenarios being completely correlated comparisons resulting in an 80% power and completely uncorrelated comparisons resulting in an 96% power for the study.

Efforts will be made to include at least 17 female subjects (approximately 40%). However, a minimum of 9 female subjects (approximately 20%) will be considered acceptable.

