17.7 Analysis of secondary endpoints

17.7.1 Equivalence in baseline-adjusted C_{max} and AUC_{0-inf}

 C_{max} and AUC_{0-inf} for each IP will be analysed for baseline-adjusted concentrations using the same model as described in Section 17.6.1.

Equivalence for each of the three NP products and at least one of the tobacco-based products will be concluded if the 90% CI for the ratio of C_{max} and AUC_{0-inf} , respectively, from the model falls within the acceptance interval of 80.00 - 125.00%.

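### The synopsis derives 38 evaluable subjects from a ratio of 1 and Section 17.2 from 0.95, and neither gives the stated 80% power under the protocol's 90% CI rule

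*Protocol*

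**What the plan says.** The synopsis (Statistical methods) begins "Using a coefficient of variation (CV) of 35%, based on previous studies", adds 80% power, a 10% significance level and bounds of 0.8 and 1.25, and concludes "with a null ratio of 1, 38 evaluable subjects will be needed". Allowing for 10% dropout, 43 are to be randomized.

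Section 17.2 bases the calculation on a 2x2 crossover analysed on the log scale. Table 17.2-1 repeats the CV of 0.35, the 10% alpha, the bounds, the dropout rate and the totals of 38 and 43. Its row "Hypothesized true geometric least square means ratio", however, gives 0.95. The comment on alpha says "Inference is drawn based on a 90% CI".

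The text below the table states: "The calculation outlined in Table 17.2-1 above renders an 80% power for one comparison" (NP 1 against one tobacco product). From that 80% it derives a range of 80% to 96% for showing equivalence to at least one of the two tobacco products.

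Section 17.7.1 sets the decision rule: equivalence is concluded if the 90% CI for the ratio "falls within the acceptance interval of 80.00 - 125.00" percent.

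**The concern.** There are two separate defects.

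- **Conflicting inputs.** The same 38 is obtained from a ratio of 1 in one place and 0.95 in the other, with every other input equal. Moving the assumed ratio from 1 to 0.95 brings it closer to the lower bound and raises the required number, so one set of remaining inputs cannot give 38 for both. The synopsis also calls its value the null ratio. In an equivalence test the null hypothesis is a ratio outside 0.80 to 1.25; a value of 1 can only be the assumed truth.
- **Alpha that does not match the decision rule.** A 90% CI inside the bounds is equivalent to two one-sided tests at 5% each. If 10% was entered as the level of each test, the calculation describes an 80% CI rule, which is easier to meet than the rule that will be applied.

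This is the protocol's only sample size justification, and it concerns the only endpoint with a formal success criterion, the first secondary one. If the stated power is too high, the chance of an inconclusive equivalence result is understated, and so is everything built on the 80%.

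**Working it through.** **Inputs.** CV 0.35, bounds 0.80 and 1.25, target power 80%, n = 38 evaluable (synopsis and Table 17.2-1); ratio 1 (synopsis) or 0.95 (Table 17.2-1); 2x2 crossover on the log scale (Section 17.2), so df = n − 2; 90% CI rule (Table 17.2-1, Section 17.7.1). The protocol does not say which CV is meant. It is taken here as within-subject, as the 2x2 crossover formula requires.

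**Formulas.**

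- Within-subject SD on the log scale: σ = √ln(1 + 0.35²) = √ln(1.1225) = 0.340.
- Standard error of a log-ratio: SE = σ·√(2/n) = 0.340 × √(2/38) = 0.078.
- Equivalence is declared if ln(0.80) + t·SÊ ≤ d ≤ ln(1.25) − t·SÊ, where d is the estimated log-ratio, SÊ is the estimated standard error and t is the (1 − α) quantile with 36 df. Here α is the level of each one-sided test: 0.05 for a 90% CI and 0.10 for an 80% CI.
- Power is the probability of that event when the true log-ratio is ln(0.95) or ln(1), integrated over the chi distribution of the residual SD.

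As a check on the method, CV 0.20, ratio 0.95, n = 20 and α = 0.05 gives 0.8347, the known reference value.

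**Reproducing the plan's figure, then applying its own rule.**

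| Level per one-sided test | Matching CI | True ratio | Power at n = 38 | Smallest n for 80% |
|---|---|---|---|---|
| 10% | 80% | 0.95 | 80.1% | 38 |
| 10% | 80% | 1 | 87.8% | 32 |
| 5% | 90% | 0.95 | 66.2% | 52 |
| 5% | 90% | 1 | 75.5% | 42 |

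Only the first row reproduces 38, and it does so exactly: 37 subjects give 79.1% and 38 give 80.1%. The likely explanation is that the nominal 10% was entered as the level of each one-sided test. The synopsis ratio of 1 does not give 38 at either level. The dropout step is correct: 38/0.9 = 42.2, rounded up to 43.

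**Sensitivity under the 90% CI rule.**

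| Variant | Ratio 0.95 | Ratio 1 |
|---|---|---|
| n = 38, five-period error df, 4(n − 1) | 67.7% (50 needed) | 77.1% (41 needed) |
| All 43 randomized evaluable, 2x2 df | 72.5% | 82.2% |

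**The 80% to 96% range.** The protocol's upper figure is 1 − 0.20² = 0.96. By the same logic, with the same true ratio against both comparators and 66.2% per comparison, full correlation gives 66% and no correlation gives 1 − (1 − 0.662)² = 0.886, about 89%. At a ratio of 1 the limits are 75.5% and 1 − (1 − 0.755)² = 0.940.

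**The case against.** The strongest reply has four parts.

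- **The synopsis may only be mislabelled.** The two places use different terms, and treating the null ratio as the assumed true ratio is an inference. That is fair, but it is the only workable reading. If it is wrong, the synopsis omits the assumed ratio altogether, and the power shortfall in Section 17.2 remains.
- **The CV is not said to be within-subject.** If 0.35 were a total CV, a within-subject correlation of roughly 0.27 on the log scale would bring power at 0.95 to about 80% under the 90% CI rule (0.25 gives 79.3%, 0.28 gives 80.9%). The assumption should therefore be stated. But the protocol mentions no such correlation, a within-subject CV is the natural reading for a 2x2 crossover calculation, and the exact match to 38 at 10% per side points to the alpha as the cause.
- **The shortfall at a ratio of 1 is small, and 38 is a lower planning bound.** The mixed model can use partial completers, and with all 43 evaluable the power at a ratio of 1 passes 80%. This stands. It does not help at 0.95, the value in the detailed section, where even 43 give 72.5%.
- **Nothing in the analysis changes.** The statement concerns a secondary endpoint; the primary similarity endpoint is judged from point estimates and descriptive statistics. The decision rule is stated consistently and holds each comparison at 5% per side. That limits the consequence to planning, but it does not make the stated power correct.

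**Conclusion.** The point holds on both counts. The synopsis and Section 17.2 give different assumed ratios for the same 38 subjects, and under the protocol's own rule neither ratio yields 80% power. The shortfall is about 14 percentage points at 0.95 (66.2%; 52 evaluable needed, or 58 randomized at 10% dropout) and about 4.5 points at 1 (75.5%; 42 evaluable, 47 randomized). The claim of at least 80% power for equivalence to one or other tobacco product is unsupported.

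These figures assume a within-subject CV of 0.35 and the 2x2 design of Section 17.2. The re-based 66% to 89% range also keeps the protocol's simplification that the same true ratio applies against both the 4 mg and the 8 mg product. Type I error, estimates and confidence intervals are unaffected.

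**What to change.** 1. Give one assumed true ratio in both places. Changing the synopsis to the 0.95 of Table 17.2-1 is the direct route; the sponsor should confirm that 0.95 is the intended value. Call it the assumed true ratio and drop the term null ratio.
2. In Table 17.2-1, state that the 90% CI rule means 5% per one-sided test, and that the CV of 0.35 is within-subject.
3. Restate the power of 38 evaluable subjects under that rule: about 66% per comparison at 0.95, with about 75% at a ratio of 1 as a sensitivity figure.
4. Replace the 80% to 96% range with about 66% to 89%, saying that it assumes the same true ratio against both tobacco products, and remove the statement that power exceeds 80%.

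The cost is wording in the synopsis and Section 17.2, and a less favourable stated power. The number of subjects can stay as planned.

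### The synopsis bases the 38 evaluable subjects on a ratio of 1, Table 17.2-1 bases them on a true ratio of 0.95, and a ratio of 1 does not give 38

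*Protocol*

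**What the plan says.** The synopsis, under Statistical methods, lists a CV of 35%, 80% power, a 10% significance level and "lower and upper equivalence bounds of 0.8 and 1.25". It concludes that "with a null ratio of 1, 38 evaluable subjects will be needed", and after 10% drop-out that 43 will be randomized. It mentions no other ratio.

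Section 17.2 gives the detailed calculation: "The sample size is calculated assuming a 2x2 crossover design analyzed on log scale". Table 17.2-1 repeats the CV, alpha, bounds, drop-out rate, 38 and 43, but its row for the "Hypothesized true geometric least square means ratio" reads 0.95. The comment on alpha is "Nominally set. Inference is drawn based on a 90% CI". The text below the table says that the calculation "renders an 80% power for one comparison of NP 1 and one of the tobacco-based products".

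Section 17.7.1 sets the decision rule: equivalence is concluded if the 90% CI of the ratio lies within 80.00 to 125.00%.

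**The concern.** The two places justify one sample size with the same inputs except the ratio, and the ratio is an input to which equivalence power is very sensitive.

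The synopsis term is also wrong in itself. In an equivalence test the null hypothesis is that the ratio lies at or beyond 0.80 or 1.25. A ratio of 1 is the centre of the alternative. If the phrase means the assumed true ratio, it contradicts Table 17.2-1. If it means the null hypothesis, it misdescribes the test, and the synopsis then gives no assumed true ratio at all, so its calculation cannot be repeated.

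Many readers go no further than the synopsis. They would take 80% power to assume exact equality of products, when the planned size already allows for a true difference of 5%.

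**Working it through.** **Inputs.** CV 0.35, bounds 0.80 and 1.25, target power 80%, nominal alpha 10% (synopsis and Table 17.2-1). 2x2 crossover on the log scale (Section 17.2). Ratio 1 (synopsis) or 0.95 (Table 17.2-1). The protocol's 10% can be read as 10% for each one-sided test, or as 5% for each, which is what a 90% CI corresponds to. Both readings are run.

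**Formulas.**
- Within-subject log-scale SD: s = sqrt(ln(1 + 0.35²)) = 0.340.
- Standard error of the log ratio with n subjects: SE = s·sqrt(2/n), with n − 2 degrees of freedom. At n = 38, SE = 0.340·sqrt(2/38) = 0.078.
- Log-scale bounds: ln 0.80 = −0.223 and ln 1.25 = 0.223.
- Distance from the assumed ratio to the nearer bound: 0.223 for a ratio of 1. For 0.95, ln 0.95 = −0.051, so the distance is 0.223 − 0.051 = 0.172.
- Power is the probability that both one-sided t-tests reject, integrated over the distribution of the estimated SD.

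**The plan's own figure.** With ratio 0.95 and 10% per side, power is 79.1% at n = 37 and 80.1% at n = 38. The 38 is reproduced exactly. Drop-out: 38/0.9 = 42.2, rounded up to 43, as stated.

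**All four combinations.**

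| Assumed true ratio | Alpha per one-sided test | Smallest n for 80% power | Power at that n | Power at n = 38 |
|---|---|---|---|---|
| 0.95 (Table 17.2-1) | 10% | 38 | 80.1% | 80.1% |
| 1 (synopsis) | 10% | 32 | 80.9% | 87.8% |
| 0.95 (Table 17.2-1) | 5% (90% CI) | 52 | 80.7% | 66.2% |
| 1 (synopsis) | 5% (90% CI) | 42 | 81.0% | 75.5% |

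**Effect of the ratio alone.**
- At 10% per side: 38 − 32 = 6 subjects, and 87.8 − 80.1 = 7.7 points of power.
- At 5% per side: 52 − 42 = 10 subjects, and 75.5 − 66.2 = 9.3 points.

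**Could another method turn ratio 1 into 38?** With the degrees of freedom of a five-period model, ratio 1 needs 31 (10% per side) or 41 (5% per side). A normal approximation gives 31 or 40, and at 5% per side its power at 38 is 77.6%. Using 0.35 directly as the log-scale SD gives 34 or 44 in the 2x2 design. None gives 38.

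**The case against.** The strongest reply is that this is a slip of terminology. The two labels differ, and Section 17.2, which holds the full derivation, states 0.95 openly and yields 38. On this view the synopsis merely summarizes a sound table badly. The trial's size, model and decision rule are unaffected. The calculation serves the first secondary endpoint, while the primary endpoint is judged from point estimates and descriptive statistics (Section 17.6.1).

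Much of this stands. The 38 was evidently computed with 0.95, and the synopsis wording does not alter the trial's actual power; the differences of 8 to 9 points measure how far apart the two stated assumptions are. It does not rescue the sentence, though: 1 is the only ratio the synopsis offers, and it is wrong either as a null or as the planning value.

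A second reply is that the figures at 5% per side belong to a different question, how the 10% is split. The ratio conflict does exist under either split. The 5% figures are still needed, because a corrected synopsis should report power under the decision rule the protocol uses. The reply is right that inserting 0.95 alone leaves the 80% claim unsupported under that rule.

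**Conclusion.** The point holds. The synopsis and Table 17.2-1 give different ratios for the same 38 subjects, and the stated number follows from 0.95, not from 1. With a ratio of 1 the synopsis inputs call for 32 or 42 evaluable subjects, depending on whether 10% or 5% is applied per side. The gap between the two ratios is 6 or 10 subjects, or about 8 to 9 points of power at n = 38.

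This rests on the protocol's own inputs: CV 0.35, bounds 0.80 to 1.25, and a 2x2 crossover on the log scale for a single comparison. It is worth correcting because one ratio must underlie one sample size. It concerns the power statement for the first secondary endpoint and does not touch the primary analysis.

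**What to change.** In the synopsis, replace the reference to a null ratio of 1 with an assumed true geometric mean ratio of 0.95, as in Table 17.2-1. In the same place, give the power that 38 evaluable subjects provide for one comparison at that ratio under the 90% CI rule, which is about 66%. If the sponsor does mean a true ratio of 1, Table 17.2-1 and the stated number and power must be revised instead. The same ratio must appear in both places.

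The cost is one sentence in the synopsis. The correction changes nothing in conduct and does not itself require more subjects. Stating the power under the 90% CI rule will, however, show that the 80% claimed in the synopsis and in Section 17.2 does not hold under that rule. Reaching 80% at 0.95 would take 52 evaluable subjects (52/0.9 = 57.8, so 58 randomized). Whether to enroll more or accept the lower power is a separate decision for the sponsor.
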